- To assess the efficacy of sipuleucel-T in reducing histopathologic reclassification to a higher Gleason grade in prostate cancer subjects on active surveillance (AS)

Secondary Objectives:

- To assess the differential receipt of local or systemic therapy (surgery, radiation, androgen deprivation therapy (ADT)) in each study arm, and the reasons for receipt of further local or systemic therapy
- To assess differences in quality of life (i.e., patient-reported outcomes (PRO)) between sipuleucel-T and control arms
- To evaluate the safety of sipuleucel-T in men with low to intermediate risk localized prostate cancer

Exploratory Objectives:

- To evaluate in the sipuleucel-T arm the association of peripheral blood and tumor microenvironment immunologic responses with reclassification of Gleason grade over time
- To evaluate clinical assessments and potential correlation to sipuleucel-T
- To evaluate prostate tissue genomics

Primary Endpoint:

- Proportion of subjects without histological reclassification (Gleason group upgrade) within 36 months of randomization as determined by Blinded Independent Central Review (BICR)
 - Upgrade is defined as subjects at randomization with either International Society of Urological Pathology (ISUP) Grade Group 1 (Gleason 3+3) upgraded to Grade Group 2 (Gleason 3+4) or higher or subjects at randomization with Grade Group 2 upgraded to Grade Group 3 (Gleason 4+3) or higher.

Secondary Endpoints:

- To determine the number of subjects with subsequent prostate cancer treatment (e.g., surgery, radiation, ADT) in each study arm

P17-1 (ProVent) Protocol

- Characterization of PROs by Memorial Anxiety Scale for Prostate Cancer (MAX-PC), Short Form 12 Health Survey (SF-12), The Expanded Prostate Cancer Index Composite for Clinical Practice (EPIC-CP), International Prostate Symptom Score (IPSS) at baseline and 12-, 24-, and 36-month visits after randomization
- To evaluate safety by determining the incidence of adverse events (AEs), assessing laboratory data for clinically significant laboratory abnormalities and evaluating physical examination (PE) findings in each study arm

Exploratory Endpoints:

- To calculate the correlation of prostate tissue and peripheral immune responses, as well as product parameters to sipuleucel-T efficacy

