Subjects who withdraw consent and discontinue from the study prior to completing the end of Active Phase study visit will undergo an Early Withdrawal visit within 30 days following discontinuation notice. Subjects are encouraged to have, as standard of care, a systematic prostate biopsy (≥ 10 cores) with or without MRI at the investigator's discretion prior to study withdrawal. The H&E and special-stained slides from this biopsy will be submitted for BICR determination of their ISUP Grade Group classification prior to study withdrawal.

After Screening assessments are completed, eligible subjects will be randomized 2:1 to the sipuleucel-T arm or the control arm. Subjects randomized to sipuleucel-T arm will undergo their first leukapheresis within 60 days of randomization and will receive 3 infusions of sipuleucel-T at approximately 2-week intervals. Subjects randomized to the control arm will be followed on AS as described in the schedule of events ([Table 2](#)).

Subjects randomized to the sipuleucel-T arm will be evaluated at 0, 2, 4, 6, 10, 14, and 26 weeks following the first infusion for:

P17-1 (ProVent) Protocol

- Immune responses (Week 0 prior to first infusion is baseline)
- All anti-prostate cancer therapies
- Concomitant medications
- AEs and serious adverse events (SAEs) (per reporting requirements for the sipuleucel-T arm)

Subjects randomized to the control arm will be evaluated (office visit or phone) at 3 months following randomization for:

- Survival status
- All anti-prostate cancer therapies
- Concomitant medications
- All AEs and SAEs

Subsequently, all subjects in the sipuleucel-T and control arms will be followed every 6 months from date of randomization for at least 36 months for:

- Immune responses (sipuleucel-T arm only)
- Survival status
- PSA levels (should be collected prior to DRE and biopsy procedures)
- DRE assessments
- Prostate cancer disease progression
- All anti-prostate cancer therapies
- Concomitant medications
- All AEs and SAEs

Note, for subjects randomized to the sipuleucel-T arm, scheduled events for the 26-week visit post first infusion and first 6-month visit post-randomization may take place on the same visit and only one set of immune samples need to be collected

During the Active Phase, all subjects in the sipuleucel-T and control arms will complete:

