- ^d Complete PE including vital signs done at the clinical site at Screening (genitourinary, skin, pulmonary, cardiovascular, neurological, gastrointestinal & musculoskeletal) and abbreviated PE per PI's discretion within 7 days prior to each leukapheresis and End of Active Phase Visit. Weight will be measured at each PE; height will be measured at Screening only.
- ^e The 26-week post-first-infusion visit and first 6-month visit post randomization may occur on the same visit day and only one set of immune samples need to be collected if the visits fall on the same day.
- ^f Survival status will not be obtained for subjects that are lost to follow up or withdrawn from the study.
- ^g PSA should be collected prior to DRE and biopsy procedures.
- ^h Any prostate cancer treatment (e.g., surgery, radiation, androgen deprivation therapy).
- ⁱ Patient reported outcomes/Quality of life questionnaire (IPSS, Max-PC, SF-12 and EPIC-CP) should be collected every 12 months (12-, 24-, and 36-month visits) prior to any procedures.
- ^j Biopsy 1 may take place between 12 months and 18 months post randomization. Biopsy 2 may take place between 33 months and 39 months post randomization.
- ^k Immune monitoring sample collection time points are calculated from the date of first infusion (note: not from randomization). Samples collected on infusion days (i.e., Weeks 0, 2, 4) will be drawn prior to starting the sipuleucel-T infusion. A single PAXGENE DNA sample is only collected at Week 0.
- ^l Blood draws for immune response analyses: 100mL total draw (90ml into NaHeparin Vacutainer for PBMC isolation and 10mL into no-anticoagulant vacutainer tubes for serum isolation).
- ^m Viral serology consists of hepatitis panel (HBsAg, HBsAb, HBcAb, HCV antibody(Ab), if Ab+ then HCV RNA), HIV-1, HIV-2 antibody screen, and HTLV-1, HTLV-2 antibodies
- ⁿ End-of-Active Phase visit will take place within 30 days following Biopsy 2.
- ^o Follow-up visits will start 6 months after the End-of-Active Phase visit.
- ^p The early withdrawal visit must occur within 30 days of the last visit.
- ^q Risk factors for cardiovascular events will include diabetes mellitus, smoking history, family history, left ventricular hypertrophy, atrial fibrillation, hypertension, myocardial infarction and other cardiovascular disease.
- ^r Chemistry and/or hematology should be completed at a local lab within 7 days of leukapheresis as requested by the Apheresis center

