7.2 Sipuleucel-T Treatment

7.2.1 Leukapheresis and Infusion Scheduling

Once a subject has completed screening assessments and has been confirmed to be eligible and randomized to the sipuleucel-T arm, Dendreon will designate a leukapheresis center and the site will request a schedule for the subject's leukapheresis procedures to occur at approximately 2-week intervals. The date of each leukapheresis procedure will determine the date for the subsequent infusion of sipuleucel-T (approximately 3 days later).

The clinical trial site will receive confirmation of the leukapheresis and infusion dates and will schedule the subject's infusion appointments accordingly. If the subject is subsequently deemed ineligible for the study, the clinical trial site will be informed and the leukapheresis and infusion appointments will be canceled.

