12.7 Safety Analyses

12.7.1 Adverse Events

A summary of AEs, including the number and percentage of events reported, and the number and percentage of subjects

- reporting at least one AE,
- with at least one grade ≥ 3 AE,
- with at least one SAE,
- with at least one study drug related AE (probable or possibly related),
- with an AE leading to death

will be presented by study treatment arm in the Safety population. In the summary by worst National Cancer Institute Common Terminology Criteria for Adverse Events (NCI CTCAE) v5.0 grade, the AE with the highest or most severe grade will be counted when subjects have multiple AEs in a SOC or PT.

A breakdown of the number and percentage of subjects reporting each kind of AE above, categorized by SOC and PT, will be also presented. This breakdown will be sorted by PT within SOC. Note that counting will be by subject and not by event and subjects are only counted once within each SOC or PT. This breakdown will be repeated and sorted by descending frequency of PTs in the sipuleucel-T arm for subjects reporting at least one AE and subjects reporting at least one grade ≥ 3 AE. This breakdown will also be

repeated by worst CTCAE grade for subjects reporting at least one AE and subjects reporting at least one grade ≥ 3 AE, sorted by PT within SOC.

AEs occurred within 1 day after any leukapheresis will be summarized. Similarly, AEs occurred within 1 day after any infusion will be summarized.

Listings of AEs will also be presented.

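### By month 6 sipuleucel-T men have about 10 scheduled AE contacts and control men 2, and the SAP starts the AE count at different points in the two arms, so the by-arm all-grade AE tables mix ascertainment with product effect

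*Protocol*

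**What the plan says.** **Contact schedule.** For the experimental arm the Protocol synopsis (Active Phase) states: "Subjects randomized to the sipuleucel-T arm will be evaluated at 0, 2, 4, 6, 10, 14, and 26 weeks following the first infusion". Table 1 also marks AEs at each of the three leukaphereses, at each of the three infusions and at every 6-month visit. Weeks 0, 2 and 4 are the infusion days: "Samples collected on infusion days (i.e., Weeks 0, 2, 4) will be drawn prior to starting the sipuleucel-T infusion". The last of these visits can be shared, since "scheduled events for the 26-week visit post first infusion and first 6-month visit post-randomization may take place on the same visit". For the other arm: "Subjects randomized to the control arm will be evaluated (office visit or phone) at 3 months following randomization for" survival status, anti-cancer therapy, concomitant medication and AEs. After that, Table 2 marks AEs at the 6-month visits, the two biopsies and the later visits, as Table 1 does.

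**Collection.** Protocol 8.8 ties AE assessment to the scheduled visits and adds assessment as needed. Protocol 9.1.4 collects AEs from randomization in both arms, with start and stop dates.

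**Analysis.** The secondary safety endpoint is worded "To evaluate safety by determining the incidence of adverse events (AEs), assessing laboratory data for clinically significant laboratory abnormalities" and is to be evaluated in each arm. SAP 12.7.1 gives the percentage of subjects with at least one AE, grade 3 or higher AE, SAE or related AE by arm, and adds: "A breakdown of the number and percentage of subjects reporting each kind of AE above, categorized by SOC and PT, will be also presented". It also plans tables of AEs within 1 day of leukapheresis and of infusion. SAP 8.4.1 defines no treatment-emergent AE. It summarizes events after first leukapheresis on sipuleucel-T and after randomization on control. No AE table is split by period.

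**The concern.** Mild, short-lived events tend to be recorded when someone asks soon after they occur. In an open-label trial, asking one arm five times as often in the first half year can raise its recorded low-grade incidence even if the product does nothing. Starting that arm's count later removes background time from it alone, which lowers its incidence. Both artefacts sit in the same table, pull in opposite directions and have an unknown net size. Readers will take percentages shown beside a randomized control as the product's effect. What is at stake is the interpretation of a secondary endpoint. The primary endpoint is not touched.

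**Working it through.** The plan gives no contact count, AE rate or recall figure, so there is nothing of its own to reproduce.

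**1. Contacts by month 6 (Tables 1 and 2).** Sipuleucel-T: 3 leukaphereses + 3 infusions + Weeks 6, 10 and 14 + the 6-month visit = 10. This holds for a first leukapheresis anywhere from day 3 to day 60. At day 60, for example, the days are 60, 63, 74, 77, 88, 91, 105, 133, 161 and 183. Control: month 3 and month 6 = 2.

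**2. Whether Week 26 is a separate visit.** It is timed from first infusion (window 7 days either way), while the 6-month visit is timed from randomization (14 days either way). The two windows meet only if first infusion is within 7 + 14 = 21 days of randomization. After a day-60 leukapheresis, Week 26 falls at 60 + 3 + 182 = day 245, about month 8. That is an additional contact after month 6.

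**3. Illustrative model (assumptions, not document figures).** Both arms have the same true background rate, one AE per man per 26 weeks. An event is recorded at the next scheduled contact with probability exp(-delay/τ), where τ is mean recall. For a gap g between contacts, the recorded mean is τ(1 - exp(-g/τ))/26. Summing over gaps gives m, and P(at least one) = 1 - exp(-m). Month 3 is week 13 and month 6 is week 26. Over 36 months I added the 6-monthly visits and Biopsy 1 at month 15, and kept Week 26 separate only for the day-60 start.

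Example, τ = 8 weeks, leukapheresis 1 at day 0:
- Control, gaps 13 and 13: m = 2 × 8 × (1 - e^(-1.625))/26 = 0.494, P = 39.0%.
- Sipuleucel-T, gaps 0.43 (three), 1.57 (two), 2, 4 (two) and 11.57: m = (1.25 + 2.85 + 1.77 + 6.30 + 6.12)/26 = 0.703, P = 50.5%.
- Difference: +11.5 points.

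**4. Results with the SAP 8.4.1 counting rule** (percent of men with at least one recorded AE, sipuleucel-T vs control; differences taken before rounding):

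| Leukapheresis 1 | τ (weeks) | 6 months | Diff. | 36 months | Diff. | Event ratio, 36 months |
|---|---|---|---|---|---|---|
| Day 0 | 4 | 42.1 vs 25.6 | +16.5 | 76.7 vs 70.1 | +6.7 | 1.21 |
| Day 0 | 8 | 50.5 vs 39.0 | +11.5 | 90.8 vs 88.6 | +2.1 | 1.10 |
| Day 0 | 16 | 56.2 vs 49.6 | +6.6 | 97.0 vs 96.5 | +0.5 | 1.04 |
| Week 2 | 4 | 41.8 vs 25.6 | +16.2 | 76.6 vs 70.1 | +6.5 | 1.20 |
| Week 2 | 8 | 49.5 vs 39.0 | +10.5 | 90.6 vs 88.6 | +2.0 | 1.09 |
| Week 2 | 16 | 54.4 vs 49.6 | +4.8 | 96.8 vs 96.5 | +0.3 | 1.03 |
| Day 60 | 4 | 38.3 vs 25.6 | +12.7 | 78.3 vs 70.1 | +8.3 | 1.27 |
| Day 60 | 8 | 43.1 vs 39.0 | +4.1 | 91.2 vs 88.6 | +2.6 | 1.12 |
| Day 60 | 16 | 45.9 vs 49.6 | -3.7 | 96.8 vs 96.5 | +0.3 | 1.03 |

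**5. Separating the two artefacts.** With no recall loss only the unequal start remains. The 6-month event ratio is then (183 - 14)/183 = 0.92 for a day-14 start and (183 - 60)/183 = 0.67 for a day-60 start. Conversely, counting from randomization in both arms turns the day-60 differences at 6 months into +20.5, +14.5 and +8.5 points. Aligning the start alone therefore uncovers the contact effect and does not remove it.

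**The case against.** The strongest reply is that the plan makes no inferential AE comparison. Protocol 10.5.2 has safety summarized descriptively, so no test is biased. That is correct, but a descriptive percentage carries the same artefact.

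A reader might infer more than the documents support:
- *Background events are bound to produce a false excess on sipuleucel-T.* They are not. This needs events to be lost between contacts, AEs may also be reported as needed, and the SAP's later start can cancel or reverse the excess.
- *The 6-month size applies to the planned table.* SAP 12.7.1 covers the whole study, where the excess is diluted.
- *Control men go unexamined.* They lack the pre-leukapheresis examinations, but both arms have a digital rectal examination at month 6, and SAP 8.4.6 sends abnormal findings to the AE form.
- *The schedules are identical after month 6.* For later starters a separate Week 26 visit can follow.
- *The artefact can never be disentangled.* Onset dates are recorded, so period tables can be made from the data already planned.

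It is also fair that the grade 3 or higher, SAE and within-1-day tables already exist. None of them is split by period, and none aligns the start of the count.

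**Conclusion.** The point holds as an interpretation problem in a descriptive secondary endpoint. The 10 versus 2 contacts and the unequal start of counting follow directly from the documents. The size does not, because it rests on the assumed rate, the assumed recall and the timing of leukapheresis. Under one background AE per man per 26 weeks and mean recall of 4 to 16 weeks, the spurious difference in men with at least one AE is about +17 to -4 points at 6 months and about 0 to 8 points over 36 months. The 36-month ratio of recorded events, which matters more for individual preferred-term rows, is about 1.03 to 1.27. With perfect recall the direction reverses. That SAEs and grade 3 or higher AEs depend less on contact frequency is a judgment, not something the documents state.

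**What to change.** In SAP 8.4.1 and 12.7.1 keep the planned tables and add the following.

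1. By-arm AE tables that count from randomization in both arms.
2. A split by onset before and after a common cut beyond which scheduled contact is equal. The cut must come after the later of the 6-month and Week 26 visits on sipuleucel-T, with a fixed equivalent time for control. Month 9 in both arms would serve: the latest Week 26 visit after a day-60 leukapheresis is day 245 + 7 = 252, and month 9 is about day 274.
3. A statement of how the tables will be read. All-grade differences between arms are read from the later period. In the early period the reading rests on SAEs and grade 3 or higher AEs. The early all-grade difference is still shown, with a note on the unequal contact and beside the planned within-1-day tables.

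There is no need to withhold the early low-grade comparison or to add contacts for control men. The cost is SAP text and a few extra tables from onset dates already recorded, plus a more cautious reading of early low-grade AEs.

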MAX-PC	Memorial Anxiety Scale for Prostate Cancer
mpMRI	multiparametric magnetic resonance imaging
OS	overall survival
NCI	National Cancer Institute
NK	natural killer cells
PAP	prostatic acid phosphatase
PA2024	recombinant fusion protein composed PAP linked to GM-CSF

P17-1 (ProVent) Protocol

PCa	prostate cancer
PBMC	peripheral blood mononuclear cells
PE	physical examination
PRO	patient-reported outcome
PSA	prostate specific antigen
SAE	serious adverse event
SF-12	Short Form 12 Health Survey
TIA	transient ischemic attack
TNC	total nucleated cell
ULN	upper limit of normal
WBC	white blood cell

1.0 REGULATORY AND GOOD CLINICAL PRACTICE REQUIREMENTS

1.1 Pre-Study Documentation

Prior to site activation in order for a clinical trial site to be able to start screening the first subject, sponsor or designee must receive:

- Signed protocol and Investigator Brochure signature pages
- Signed Form FDA 1572 Statement of Investigator
- Current curriculum vitae for Investigators
- Current medical license(s) for Investigators
- Signed financial disclosure form from Investigators
- Institutional Review Board (IRB) approval letter for the protocol, informed consent form(s) (ICFs), and materials for subject information and recruitment, as applicable
- IRB-approved ICFs
- IRB membership listing or Department of Health and Human Services (DHHS) Assurance Number

All documentation must be updated as applicable throughout the study.

1.2 Institutional Review Board

The Principal Investigator is responsible for ensuring that this protocol and relevant supporting information are submitted to the appropriate IRB for review and approval before the study is initiated. Amendments to the protocol will also be submitted to, and approved by, the IRB prior to implementation of any change(s). The Principal Investigator is also responsible for informing the IRB of the progress of the study and for obtaining annual IRB renewal. The IRB must be informed by the Principal Investigator when the study is complete and should be provided with a summary of the results of the study as required by the IRB.

1.3 Investigator Obligations

The Principal Investigator will ensure all clinical trial site personnel conduct the study in compliance with ethical principles contained within the Declaration of Helsinki, the International Conference on Harmonization (ICH) E6(R2) Guideline for Good Clinical Practice (GCP), and the Food and Drug Administration (FDA) Guidance for Industry: Good Pharmacovigilance Practices and Pharmacoepidemiologic Assessment ([FDA 2005](#)). The investigator will follow all national, state, and local laws.

The Principal Investigator will be responsible for the subject's compliance with the study protocol, and must meet periodically with the sponsor or designee's study monitor.

All investigators listed on Form FDA 1572 must complete financial disclosure forms (including information on spouses, legal partners, and/or dependent children). Investigators must promptly update this information if any relevant changes occur in the course of the study or in the year after the study is completed. Investigators must also complete a new financial disclosure form throughout the study per sponsor or designee's requirement, regardless of whether any information has changed.

In addition, the Principal Investigator is responsible for providing the sponsor or designee an adequate final report shortly after study participation is complete.

1.4 Informed Consent

Investigators are responsible for obtaining written informed consent from subjects prior to initiation of any study procedures. The investigator or an appropriately qualified delegate will obtain informed consent, document the steps of the informed consent process in the subject's medical record, and provide a copy of the signed ICF to the subject.

The ICF, including any amendments, must first be reviewed and approved by the sponsor or designee and then by the designated IRB prior to use in the study.

If an amendment to the protocol changes the subject participation schedule in scope or activity, or increases the potential risk to subjects, the ICF will be revised and submitted to the IRB for review and approval. The revised ICF must be used to obtain informed consent from subjects currently participating in the study if the information is relevant, or per the IRB's instructions. The revised ICF will be used to obtain informed consent from any new subject who is enrolled in the study after the IRB approval date of the amendment.

1.5 Subject Confidentiality

Subjects' medical information obtained as a result of this study is considered confidential, as defined by applicable local, state, and federal law, and disclosure of this information to third parties other than those noted below is prohibited. Subject identifiers (e.g., name, initials, or date of birth) will be kept confidential. A subject's medical information may be given to the subject's personal physician or other appropriate medical personnel responsible for the subject's welfare. Data generated as a result of this study will be available for inspection on request by the FDA or other regulatory authorities, sponsor or its representatives, or the IRB. Sponsor or designee may retain subjects' medical information with subject identifiers redacted.

Subject identifiers will not be collected on electronic case report forms (eCRFs) maintained by the sponsor or designee with the exception of date of birth and the Chain of Identity (COI) number of each sipuleucel-T infusion. Subject identifiers will not be disclosed in any publication related to this study.

Because sipuleucel-T is an autologous product, a unique COI number for each sipuleucel-T product must be maintained from the time of initial collection of blood during leukapheresis until infusion, to ensure each subject receives the correct product. Dendreon uses a COI number and the subject's full name and date of birth for this purpose. The COI for sipuleucel-T begins when the subject is scheduled for sipuleucel-T infusion and is referenced during leukapheresis, maintained through the manufacturing process, and finally, referenced prior to infusion. The COI number and subject's full name and date of birth will be revealed to Dendreon scheduling, manufacturing, and leukapheresis personnel. This disclosure is critical to ensuring subjects' safety.

